BNT162b2 is currently authorized under the FDA EUA for persons 5 – 15 years of age and approved for persons 16 years of age and older, while the mRNA-1273 is approved for persons 18 years of age and older. CDC's Advisory Committee on Immunization Practices (ACIP) has recommended use of these vaccines, according to the specifications in the EUAs; CDC has also published interim clinical considerations for use of COVID-19 vaccines^{17,18}. Both vaccines are administered intramuscularly with the Pfizer-BioNTech vaccine (30 µg, 0.3mL each for persons

≥ 12 years of age and 10 µg, 0.2mL each for persons 5-11 years of age) being administered 21 days apart and the Moderna vaccine (100 µg, 0.5mL each) being administered 28 days apart as a primary series in particular, for populations that include moderately or severely immunocompromised, adults over 65 years of age and those who need rapid protection against COVID-19. Doses should not be administered earlier than recommended but if given within a 4-day period prior to the scheduled time may be considered valid. The second dose can be administered between 3 and 8 weeks after the first dose for the Pfizer- BioNTech vaccine and between 4 and 8 weeks after the first dose for the Moderna vaccine. The vaccines are not considered to be interchangeable, however under extenuating circumstances such as when the brand of the first dose of vaccine is unknown, any mRNA COVID-19 vaccine may be administered 28 days following the first dose¹⁷.

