In a study comparing the safety and immunogenicity of BNT162b2 vaccine in adolescents to that in adults local and systemic events were generally mild to moderate in severity and were reported at similar frequencies in both age cohorts. As with adults, systemic events were reported more often after BNT162b2 dose 2 than after dose 1. The vaccine produced a greater immune response in adolescents than adults and was highly effective²⁷.

A study assessing two 10 µg doses of BNT162b2 in children 5 to 11 years of age each administered 3 weeks apart, showed the vaccine to be safe, immunogenic and efficacious in this age group as well. Solicited injection site and systemic reactions were generally mild to moderate and lasted 1 to 2 days. In general, systemic events were reported more commonly after the second dose than the first dose. Fever occurred in 8.3% of recipients after the first and second dose.²⁸

Hypersensitivity Reactions and mRNA COVID-19 Vaccines

In the Pfizer mRNA phase III trial, more participants reporting hypersensitivity-related adverse events in the vaccine group (137 [0.63%]) compared with the placebo group (111 [0.51%]). There were no anaphylactic or severe hypersensitivity reactions reported (FDA EUA).

In the Moderna mRNA COVID vaccine phase III trial, more participants reported hypersensitivity-related adverse events in the vaccine group 1.5% of vaccine recipients (258 events in 233 participants) compared with the placebo group 1.1% of placebo recipients (185 events in 166 participants). There were no anaphylactic or severe hypersensitivity reactions with close temporal relation to the vaccine. There was one anaphylactic reaction occurring 63 days after the second dose of the vaccine that did not meet the Brighton Collaboration Anaphylaxis Case Definition (FDA EUA).

There have been numerous reports of anaphylactic reactions after the Pfizer and Moderna vaccine after the start of vaccination campaigns (MMWR January 22, 2021, Vol. 70; MMWR January 15, 2021, Vol. 70). The update on anaphylaxis reports to VAERS following mRNA COVID Vaccines through January 18, 2021 (January ACIP meeting), showed following results:

Table 4. Anaphylaxis reports to VAERS following COVID-19 vaccines.

Characteristic	Pfizer-BioNTech (N = 50)	Moderna (N = 21)
Median age, years (range)	38.5 (26-63)	39 (24-63)
Female (%)	47 (94)	21 (100)
Minutes to symptom onset, median	10	10

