The geometric mean  $ID_{50}$  and  $ID_{80}$  titers pre- and post-vaccination with mRNA COVID-19 will be compared (within vaccine group pre versus post and between vaccination groups) using a regression model adjusting for vaccine platform (Pfizer or Moderna) and study site with the log transformed titer geometric mean  $ID_{50}/ID_{80}$  values at the two-sided alpha 0.05 level. Should there exist a substantial difference (based on a statistical evaluation of these data) in titer values between the vaccine platforms, these proposed analysis and tables will be done within vaccine platform type (i.e., separate analyses for Pfizer or Moderna). This decision will be made with the study team once all data have been collected and are ready for analysis. Tables will be generated to present the geometric mean raw  $ID_{50}$  and  $ID_{80}$  values pre- and post-vaccination by vaccination group.

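### The EO8 titre analysis drops its pooled between-arm comparison on the strength of a platform difference that the model already adjusts for, judged after the data are in and without a stated test or threshold

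*SAP*

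**What the plan says.** SAP 8.3, EO8, compares geometric mean ID50 and ID80 titres within and between vaccination groups on the log scale, "using a regression model adjusting for vaccine platform (Pfizer or Moderna) and study site", with "values at the two-sided alpha 0.05 level". This serves the statement in SAP 4.2.2.2 and Protocol 3.2.2.2 that neutralising titres will be compared between the Simultaneous and Sequential groups for each variant tested.

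The next sentence makes that model conditional. "Should there exist a substantial difference (based on a statistical evaluation of these data) in titer values between the vaccine platforms", then "these proposed analysis and tables will be done within vaccine platform type (i.e., separate analyses for Pfizer or Moderna"). On timing and authority the SAP says: "This decision will be made with the study team once all data have been collected and are ready for analysis".

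The text does not state which test or threshold defines substantial, whether it applies to titres before or after vaccination, which variant it uses, or whether it uses ID50 or ID80. It does not say whether the decision is made blind to arm. It names no pooled or recombined estimate to be kept once the analyses are separated.

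**The concern.** The switch looks at the wrong quantity. If titres run higher on one platform, that is a platform main effect, and the planned covariate takes it out of the between-arm comparison. A single pooled arm effect becomes questionable when the arm effect itself differs between platforms, which is an arm-by-platform interaction. EO8 does not examine one.

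Platform is also not randomised: SAP 4.4 stratifies by age, vaccine series and site only. A platform difference may therefore partly reflect who received which product. Protocol 1.1 describes BNT162b2 from age 5, "while the mRNA-1273 is approved for persons 18 years of age and older", and reports of BNT162b2 that "The vaccine produced a greater immune response in adolescents than adults".

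At stake is the overall estimate of whether co-administration changes SARS-CoV-2 titres. Once the switch is applied, the reader has two subset estimates with wider intervals and no planned way to combine them. Because the criterion is undefined and applied with the data in hand, an outside reader also cannot tell whether it was met.

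**Working it through.** **Figures in the documents.** The only power figure is for the primary reactogenicity endpoint (Protocol 7.1.1, SAP 4.3): 15% in the Sequential group, margin 10 points, 214 per group, one-sided alpha 0.025, power 82.6%. It reproduces: 0.10 / √(2 × 0.15 × 0.85 / 214) = 2.897; 2.897 − 1.960 = 0.937; Φ(0.937) = 82.6%. It says nothing about EO8. For EO8 the documents give no power, titre SD, target ratio, expected platform difference or Pfizer:Moderna split.

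**Assumptions used below.** Equal residual SD on both platforms, arms balanced 1:1 within platform, normal approximation, two-sided 5% tests. Where a sample size is needed, 214 per arm. That is optimistic, because EO8 uses the Immunogenicity Population (Protocol 7.1.8), whose size is not given.

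**Step 1: interval width.** A platform holding a share s of participants has an interval wider by a factor 1/√s.

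- s = 0.50: 1.41
- s = 0.65: 1.24
- s = 0.35: 1.69

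**Step 2: power within a platform.** Let the arm effect have 80% pooled power, so its standardised size is 1.96 + 0.84 = 2.80. Power in a share s is Φ(2.80√s − 1.96).

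| Share s | 2.80√s − 1.96 | Power |
|---|---|---|
| 0.50 | 0.02 | 51% |
| 0.65 | 0.30 | 62% |
| 0.35 | −0.30 | 38% |

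**Step 3: dependence on the effect size.** With 214 per arm, 80% pooled power corresponds to a log10 difference of 2.80 × SD × √(2/214) = 0.271 × SD. For an assumed log10 SD of 0.4 to 0.6, that is a titre ratio of 1.28 to 1.45. For a two-fold arm difference at SD 0.6 and 107 per arm: 0.301 / (0.6 × √(2/107)) = 3.67, and power is Φ(3.67 − 1.96) = 96%, against more than 99% pooled. At a 65:35 split the smaller platform (about 75 per arm) keeps about 87%. Large effects survive the split; modest ones do not.

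**Step 4: counting a hit on either platform.** At 50:50 the chance of at least one significant result is 1 − (1 − 0.508)² = 76%, close to the pooled 80%. The price is the false-positive chance: 1 − 0.95² = 9.75% instead of 5%, for each variant and each of ID50 and ID80.

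**Step 5: would the switch be used?** Suppose the statistical evaluation were a two-sided 5% test on 428 people, with SD 0.4 to 0.6 and splits from 50:50 to 80:20. It would fire with probability Φ(log10(ratio) / (SD × √(1/nP + 1/nM)) − 1.96), where nP and nM are the numbers on each platform: 27–71% at a true platform ratio of 1.25, 68–99% at 1.5, and about 99–100% at 2. The true ratio is not in the documents, so this shows sensitivity and is not a forecast.

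**The case against.** The best defence is that EO8 is exploratory, has no hypothesis or margin, and is one of many comparisons tested at 0.05 without adjustment. That stands, and it limits the weight of the point.

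Second, platform-specific results have uses. EO8 also makes pre-versus-post comparisons within group, and pooled geometric means there depend on the product mix. Unequal residual variance could also favour separate models. Both are fair reasons to show platform-specific tables. Neither is a reason to withhold the pooled arm estimate.

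Third, several stronger readings are tempting but not supported:

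- *The switch is automatic.* It is not. The text requires a substantial difference and a study-team decision. The defect is that neither is defined.
- *The switch is likely to be used.* No document gives titres by platform. The primary-series dose contrast (30 or 10 µg against 100 µg) does not settle it: Protocol 1.1 gives a 50 µg Moderna booster, and Protocol 1.2 expects most adults and many children to be booster recipients. If a higher dose raises titres, that would favour Moderna, while stronger adolescent responses would favour Pfizer, so the two could offset. The product–age link may also loosen, since Protocol 1.2 and 3.1 allow for later approvals and new vaccines.
- *The comparison loses a fixed amount of power.* The loss depends on the assumed pooled power and split, and it applies to each platform test alone.
- *The team will choose the analysis by its result.* A platform contrast says little about the arm contrast in a 1:1 randomised trial, and nothing suggests that intent. What remains is that the SAP neither requires a blinded decision nor sets a criterion that could be checked later.
- *All antibody comparisons are affected.* The EO8 seropositivity analysis has its own site-stratified Mantel-Haenszel method, and the switch does not clearly reach it.

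**Conclusion.** The point holds for the EO8 between-arm titre regression. From the text alone, without any assumption, the trigger is a main effect already in the model; it is undefined; it is decided after data collection; and no overall arm estimate is kept.

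The size is conditional. For an arm effect with 80% pooled power, the loss within a platform is 29 points on each side at 50:50, and 18 and 42 points at 65:35. It is only about 4 points or less for a two-fold effect at 50:50 under the assumed SDs. These figures rest on an assumed split, SD, sample size and common residual variance.

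This is a worthwhile, cheap correction to one exploratory, unpowered analysis. It does not touch any primary or secondary result.

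**What to change.** In SAP 8.3, EO8, delete the conditional sentence and the one on the study-team decision, and state instead:

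1. The main between-arm titre comparison is always the pooled regression of log titre adjusted for platform and site.
2. An arm-by-platform interaction estimate with its 95% CI is reported in every case. It should be described and not used as a gate, because it will be imprecise: its standard error is √(1/s + 1/(1 − s)) times that of the pooled arm effect, which is 2.0 at 50:50 and 2.1 at 65:35.
3. Platform-specific geometric means, pre/post changes and arm ratios are always shown as supportive results, whatever the platform difference.

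The cost is a few sentences and one model term, with no new data. Every platform-specific table is retained. The one thing given up is that platform-specific arm comparisons become supportive only.

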## **9 SENSITIVITY ANALYSIS**

If any participant in the Full Analysis Population 1 receives the incorrect study product (IIV4 and placebo switched), then a sensitivity analysis will be performed based on the actual study product received for Primary Objective and Secondary Objectives 1 and 2.

## **10 INTERIM SAFETY DATA REVIEW**

The safety data review will provide the study the opportunity to identify unexpected safety concerns and make changes to the protocol if needed. The interim safety data review will be done by a safety monitoring panel with relevant expertise, comprised of experts who are not co-investigators on this study. The safety population for the interim safety review will include participants who were enrolled and randomized. The safety monitoring panel will review blinded group results (number and percent) of solicited local and systemic reactogenicity events as well as the number and percent of SAEs along with clinical narratives. If the CDC and study investigators determine additional analyses or reviews are needed, efforts will be made to conduct additional analysis or reviews that will not include analyzing the primary endpoint as a first step. This is to avoid introducing bias or increasing sample size needs for statistical power.

### Major Protocol Violations for Influenza and SARS-CoV-2 Immunogenicity Analysis

1. Major Protocol Violations for Exclusion from Immunogenicity Populations:
  - a. Not all study vaccines received
  - b. No pre- and/or post-vaccination blood draw or insufficient volume for assay analysis for respective vaccine\*
  - c. Receipt of any other vaccine between the pre- and post-vaccination blood draws
  - d. New immunosuppression disorders between the pre- and post-vaccination blood draws or receipt of immunosuppressive medication between the pre- and post-vaccination blood draws
  - e. Subject who was inadvertently enrolled and randomized to the study, though they were later learned to have had met the following criteria (see f-k below) for study exclusion that would have affected immunogenicity
  - f. Influenza vaccine receipt during the current influenza season prior to study enrollment
  - g. COVID-19 vaccine prior to enrollment unless presenting for a booster dose
  - h. Prior receipt of non-mRNA COVID-19 vaccine
  - i. Use of oral or parenteral corticosteroids ( $\geq 20\text{mg/day}$  prednisone equivalent) or high-dose inhaled glucocorticoid for  $\geq 14$  consecutive days within the preceding 30 days
  - j. Has an active neoplastic disease (excluding non-melanoma skin cancer), a history of any hematologic malignancy
  - k. Has a history of receiving immunoglobulin or other blood product (with exception of Rh immunoglobulin) within the 3 months prior to study vaccination or during the study including Evushield or other COVID-19 monoclonal antibody.
  - l. Subject who was enrolled for both the 2021-22 and 2022-23 flu seasons may be included in immunogenicity for the 2021-2022 season only.

\*Blood draws will not be considered out of window as long as blood was collected within -7/+14 days of the protocol window for the respective vaccine

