7.1.8 Exploratory Objectives

The analysis for the exploratory objectives will be detailed in the comprehensive Statistical Analysis Plan. The Immunogenicity Population will be the primary analysis population for exploratory HAI and COVID immunogenicity objectives.

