### 4.4 Randomization

Participants will be randomized (1:1) to receive either IIV4 or saline injection by an unblinded vaccinator at Visit 1. Those receiving IIV4 at visit 1 will receive saline placebo at Visit 2 and those receiving saline placebo at Visit 1 will receive IIV4 at Visit 2. Randomization will be stratified by age (5 to < 12 years of age, 12 to < 18 years of age, 18 to <65 years of age, and ≥ 65 years of age) and receipt of either a primary two-dose series or booster dose of mRNA COVID-19 vaccine (for the ≥18 age groups) using a permuted block randomization scheme stratified by Lead and Contributing Sites. The project statistician will generate permuted block randomization schemes which will be uploaded to REDCap. The randomization schedule will not be available to the study staff, so the next randomization allocation will not be known before randomization occurs. Following confirmation of study eligibility criteria during Visit 1, participant randomization will be through REDCap with treatment allocation recorded on the unblinded vaccinator CRF. In the event that REDCap is unavailable, manual randomization will occur through the use of envelopes. The project statistician will prepare 10 envelopes per age group and vaccine series per site (total of 60 per site) that will use the same randomization strategy as the primary scheme embedded in REDCap. When an unblinded team member is informed of the age group, he/she will pull the next envelope in order. In order to capture the allocation per subject, a separate form in REDCap will be used by the unblinded personnel to add the assignment. A log will need to be kept at the site capturing these instances.

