#### **6.3 Immunogenicity Population**

This population defined as subjects who received vaccine, provide baseline and Visit 3 and Visit 4 blood draws of acceptable volume and quality within the protocol-defined time frame for the respective vaccine with no protocol violations affecting immunogenicity. Protocol violations affecting the immunogenicity analyses are defined in the Statistical Analysis Plan (SAP) Appendix 1. The acceptable visit window for sample analysis will be -7/+14 days from the target date. Any subject with sufficient data for either or both of the influenza and SARS-CoV-2 analysis will be included in this population. Should 10% or more of the total study population be excluded from the Immunogenicity Population due to missing the visit window,

then an additional analysis will be performed including these subjects with the missing visit window exclusion.

The Full Analysis Population 1 is the primary population for analysis unless otherwise stated.

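### SAP Appendix 1 item 1a and the two-draw rule in SAP 6.3 are not vaccine-specific, contradict the either-or-both inclusion sentence, and can discard complete titres in the exploratory immunogenicity analyses

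*SAP*

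**What the plan says.** SAP Appendix 1 is a single list for the influenza and the SARS-CoV-2 analyses, introduced as "Major Protocol Violations for Exclusion from Immunogenicity Populations". Its first item is "Not all study vaccines received". Its second item, by contrast, is tied to one vaccine: "No pre- and/or post-vaccination blood draw or insufficient volume for assay analysis for respective vaccine". The footnote on blood-draw windows is tied to the respective vaccine in the same way.

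SAP 6.3 makes this list part of the population definition. It also requires that participants "provide baseline and Visit 3 and Visit 4 blood draws of acceptable volume and quality". The same section then states: "Any subject with sufficient data for either or both of the influenza and SARS-CoV-2 analysis will be included in this population". Protocol 7.1.2 has the same draw requirement and the same inclusion sentence.

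Protocol 7.1.8 assigns this one population to both assays: "The Immunogenicity Population will be the primary analysis population for exploratory HAI and COVID immunogenicity objectives".

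The Visit 2 injection differs by arm (SAP 4.4). In the Simultaneous arm: "Those receiving IIV4 at visit 1 will receive saline placebo at Visit 2". In the Sequential arm: "those receiving saline placebo at Visit 1 will receive IIV4 at Visit 2". Neither document defines *study vaccines*. The visit descriptions in Protocol 5.1 use *study product* for IIV4 or placebo.

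**The concern.** The population rules give different answers for the same participant. Item 1a excludes on any missed vaccine, the definition in 6.3 excludes on either missed draw, and the inclusion sentence admits anyone with enough data for one assay. Two programmers could build different sets, and the choice would be made after the data are in.

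Two things are at stake. First, valid titres can be lost for reasons unrelated to the vaccine under study. In some cases the reason is an event that happens after the titre was measured. Second, these are exclusions after randomisation. Because the Visit 2 injection is active in one arm and saline in the other, a rule that counts missed vaccines can act unequally between arms in the EO8 comparison. If missing that injection follows a reaction, it may be related to immune response.

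No planned analysis would show the effect. The additional analysis in SAP 6.3 is triggered only by window misses, and the sensitivity analysis in SAP 9 covers only switched products, for the primary objective and SO1 and SO2.

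**Working it through.** **The plan's own figures.** The documents give no sample size or power for immunogenicity. The general inputs in SAP 4.3 are consistent: 450 × 0.95 = 427.5, stated as 428, or 214 per group. The primary power also reproduces: SE = √(2 × 0.15 × 0.85 / 214) = 0.0345, and Φ(0.10 / 0.0345 − 1.96) = 0.826, against 82.6% stated. The present point does not depend on that power, so the rules were checked case by case.

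**Timing (Protocol 5.1, Tables 5 to 7).** Visit 3 is 28 days after Visit 1 (Day 29). Visit 4 is 28 days after Visit 2 (Day 36–43). Dose 2 of a primary series falls on Day 22–57 (BNT162b2) or Day 29–57 (mRNA-1273), and Visit 5 is 28 days after dose 2. By this timing, the 28-day post-IIV4 sample is Visit 3 in the Simultaneous arm and Visit 4 in the Sequential arm. The 28-day sample after the Visit 1 COVID-19 dose is Visit 3 in both arms.

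**Who is excluded.**

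| Participant | Item 1a and 6.3 read literally | Either-or-both sentence |
|---|---|---|
| A. Leaves the study before Visit 2 | Out in both arms: no follow-up blood | Out in both arms |
| B. Primary series, stops before Visit 2, no dose 2 | Out in both arms under 1a | Depends on the blood given |
| C. Primary series, has IIV4 and its 28-day sample, no dose 2 | Out in both arms under 1a | In for HAI |
| D. Simultaneous, all vaccines, baseline and Visit 3, no Visit 4 | Out under 6.3 | In for both assays |
| E. Booster, misses the Visit 2 injection, gives all later blood | Sequential out under 1a; Simultaneous stays only if placebo is not a study vaccine | In for SARS-CoV-2 in both arms; in for HAI in the Simultaneous arm only |

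In case C, dose 2 can be due as late as Day 57, after the HAI sample at Day 29 or Day 36–43. The exclusion can then rest on something that happened after the HAI endpoint was measured. In case D, the missing sample serves neither 28-day comparison. In case E, the Sequential participant has no post-IIV4 response to lose, so only SARS-CoV-2 data are discarded.

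**Size of case C.** Lost = 450 × s × k, where s is the primary-series share and k the proportion skipping dose 2. Neither is in the documents. Assuming s = 10–50% and k = 2–10%:
- low: 450 × 0.10 × 0.02 = 0.9 (0.2%)
- high: 450 × 0.50 × 0.10 = 22.5 (5.0%)

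The additional-analysis trigger is 10% of 450 = 45 and counts only window misses.

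**Size of case E.** Sequential-only exclusions = 225 × 0.05 × b × f. The 5% is the plan's dropout allowance, b is the booster share (assumed 50–100%) and f is the proportion of those dropouts who miss the Visit 2 injection but still give blood (0–100%).
- f = 0: none
- b = 0.5, f = 0.5: 2.8
- b = 1, f = 1: 11.25

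At the upper extreme, suppose the removed 5% have ID50 titres 2-fold above the rest (an assumption). The mean log2 titre in the Sequential arm falls by 0.05, and the GMT is multiplied by 2^(−0.05) = 0.966, a fall of about 3%.

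**Size of case D.** The documents give no rate for a missed Visit 4, so no count can be given.

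**The case against.** The strongest reply is that the inclusion sentence in SAP 6.3 already rescues the usable data, and that the Appendix speaks of populations in the plural and uses the respective-vaccine wording elsewhere. This supports reading the intention as vaccine-specific, but it does not settle the text. Item 1a lacks the qualifier that the next item has. Read literally, the vaccine and draw requirements would also leave the inclusion sentence with almost nobody to act on.

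A reader might infer that item 1a removes early stoppers in the Sequential arm only, and from all immunogenicity analyses. The documents do not support that. Those who leave have no follow-up blood in either arm. Primary-series stoppers lack dose 2 in either arm. A Simultaneous booster recipient who stops after Visit 1 and gives only the Day 29 sample also fails the two-draw rule. The asymmetry needs someone who declines the Visit 2 injection yet gives every later sample, or a loose reading of 6.3 beside a strict reading of 1a. It disappears if placebo counts as a study vaccine, although Simultaneous participants with complete data would then be dropped for missing saline.

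Two further points stand. A Sequential participant without IIV4 received COVID-19 vaccine alone by Day 29, so excluding that person from a comparison of simultaneous with sequential administration is a defensible choice. And dose 2 may be given as standard of care (Protocol 5.3.1), so it is unclear whether it is a study vaccine at all. That ambiguity is itself a reason to define the term.

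**Conclusion.** The inconsistency is real and decides who is analysed. Item 1a and the two-draw rule both conflict with the either-or-both sentence. Read literally, they remove complete HAI data in both arms when dose 2 is skipped, and they remove Simultaneous participants who lack only a sample taken 28 days after placebo.

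The size is modest. The dose 2 limb is about 1 to 23 of 450 under assumed shares and skip rates. The possible arm imbalance in EO8 is 0 to about 11 of 225. It is 0 if early stoppers leave the study, and the upper end needs the whole dropout allowance to be booster recipients who still give blood. Even then, an assumed 2-fold titre difference moves the GMT by about 3%.

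Only exploratory EO7 and EO8 are affected, and Protocol 6.2 makes HAI testing contingent on further funding. The primary analysis uses Full Analysis Population 1 and does not change. The correction should still be made before analysis, because it removes a choice that would otherwise be made with data in hand.

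**What to change.** 1. Reword item 1a to: *respective vaccine not received before its post-vaccination sample*. State whether placebo counts as a study vaccine.
2. Define two sets in SAP 6.3 and align Protocol 7.1.2:
   - HAI set: IIV4 received, baseline sample, and the sample 28 days after IIV4 (Visit 3 for Simultaneous, Visit 4 for Sequential), regardless of dose 2.
   - SARS-CoV-2 set: Visit 1 COVID-19 dose received, with baseline and Visit 3 samples. Dose 2 and Visit 5 are required only for post-dose-2 analyses.
3. Report EO8 with and without Sequential participants who did not receive IIV4, since either choice can be defended.

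The cost is SAP and protocol wording and a second population flag; no new data are needed. There are two downsides. EO7 and EO8 will have different denominators. In the HAI set, a Sequential participant who never received IIV4 cannot enter, while a Simultaneous counterpart with a Visit 3 sample can. That asymmetry should be stated when EO7 is reported.
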